Primary Outcomes. Adherence will be determined by the number of participants completing the 12-week intervention. We expect >80% of enrolled participants to complete the 12-week trial. Additionally, we will determine the number of participants who consistently maintain a level of nutritional ketosis (average ketones ≥ 0.5 mM).

The primary efficacy outcome will be depression score as assessed by PHQ-9 and HRSD. The self-reported PHQ-9 is a measure of depression symptom severity. It maps onto DSM-5 criteria for Major Depressive Disorder and is widely used in both clinical and nutrition research settings. The HRSD is an observer-rated measure of depression mostly used in research settings; the HRSD will be used to provide objective and standardized ratings of symptom severity, including ratings

that require external observation such as psychomotor retardation. The PHQ-9 and HRSD will be administered bi-weekly to provide a trajectory of depression symptoms.

Secondary Outcomes. In addition to changes in symptoms of depression, we will assess changes in a number of metabolic markers and cognitive markers of psychological health. We will assess the following to quantify these changes: Body weight, body composition, blood pressure, glucose, insulin, HbA1c, chemistry panel, lipids, and cognitive measures, structural and functional brain MRI). To examine changes in inflammation, we will assess the following markers: interleukin 1, interleukin 6, C-reactive protein, tumor necrosis factor-alpha, and WBC count with differential.

PARTICIPANTS

We expect to enroll up to 60 young adults with major depression into a KD intervention over a 12-week period. Participants will be able to pick up study fliers or will be handed fliers by CCS team members. Study fliers will include all inclusion and exclusion criteria and will provide potential participants with research team contact information. Participants must meet all inclusion criteria and none of the exclusion criteria as indicated on a prescreening checklist before baseline testing. Pre-screening and BL inclusion/exclusion criteria is outlined below.

Inclusion Criteria:

- OSU students (age 18-30 years at the time of enrollment) with confirmed major depressive disorder as determined by SCID-5 diagnosis at baseline testing.
- Currently engaged in counseling treatment for depression at CCS
- Available for a 12-week period and indicate willingness and ability to eat KD foods as prescribed

Exclusion Criteria:

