Baseline	3a	Weight, Hydration Status, Body Composition Testing, Survey/Side Effects, Venous Blood Draw, Body Composition, and Blood Pressure.	1 hr
Baseline	3b	Cognitive testing	1 hr
Baseline	3c	Dietary consult	45 min
Baseline	3d*	MR Testing	1 hr

5	4	Continuous Glucose Monitor / Continuous Ketone Monitor application	5 min
6	5	Weight, Hydration Status, Body Composition Testing, Survey/Side Effects, Venous Blood Draw, and Blood Pressure.	1 hr
11	6	Continuous Glucose Monitor / Continuous Ketone Monitor application	5 min
12	7a	Cognitive Tests	1 hr
12	7b	Weight, Hydration Status, Body Composition Testing, Survey/Side Effects, Venous Blood Draw, and Blood Pressure.	1 hr
12	7c*	MR Testing	1 hr

Testing Visits. As detailed in Tables 1 and 2, PHQ-9 data will be collected at baseline and bi-weekly by means of an internet-based survey and questionnaire administration program (REDCap / Qualtrics). HRSD data will be collected in-person or virtually by study assessors at baseline, 6- and 12-weeks. As part of their standard counseling protocol, counselors will also administer the CCAPS-34 to assess global mental health at baseline and 3-wk intervals. Other outcomes will be assessed at baseline, 6- and 12-weeks at a single visit in the PAES Building centrally located on the OSU campus (see **Fig 1**).

For testing at the PAES (**Fig 2**), subjects will arrive to the lab in the morning after an overnight fast. We will test for hydration, measure height and body mass, and then have participants complete surveys followed by resting blood pressure. A phlebotomist will obtain blood samples from a forearm vein in subjects after sitting for 10-min. Appropriate sample tubes will be used for EDTA, sodium heparin, or serum for different analytes. A serum tube will be sent to Quest Diagnostics to assess standard chemistry panel (liver enzymes, kidney function, lipids, etc.).

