Serum and plasma will be immediately centrifuged and aliquoted into tubes and stored at -80°C until subsequent analyses. Samples will be thawed only once for analysis and assayed in duplicate for ketones, glucose, and insulin, which will be used to calculate an index of insulin resistance, and HbA1c. Extra serum and plasma will be archived for future analysis of biomarkers that may provide insight into novel associations with depression. We will determine body composition from a single whole-body scan using dual-energy x-ray absorptiometry (iDXA, Lunar Corporation, Madison, WI). Finally, subjects will complete a battery of computerized cognitive tests. Total time for this visit will be less than 2-hours.

[figure not shown]
[figure not shown]

Fig. 2 test day timeline. Created with BioRender.com

Neurocognitive test materials and procedure. Testing sessions will be administered by trained lab staff. All participants will complete an assessment of cognitive function with the NIH Toolbox (IPAD-based assessments that examines cognitive function) and standardized neuropsychological testing (such as sub-tests from the Delis-Kaplan Executive Function System, Stroop Color Word Test, and Wechsler Memory Scale). Computer-based testing of memory (pictures and words) and executive function (attending to visually presented stimuli, such as scenes) may also be administered.

The gradCPT contains grayscale photographs of mountain scenes and city scenes. Scene images gradually transition from one image to the next^{31,32}). Participants are instructed to press the space bar on the keyboard for each city scene, and to withhold responses for mountain scenes. Practice trials will be given prior to the start of the task with feedback for each trial response to ensure that the task instructions were understood. The actual task lasts approximately 4 minutes and feedback is not provided during the task.

A. Illustration of gradCPT. Scenes gradually transition from one image to the next image. Participants are instructed to respond to city scenes and withhold for mountain scenes (Esterman et al., 2012).

MRI Image Acquisition (approximately 60 min). Participants who are MRI-eligible may volunteer for pre- and post-intervention MRI. We have the resources to complete pre- and post- intervention

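### HbA1c, a named secondary outcome, is assigned to thawed serum and plasma, which contain no red cells and cannot yield it

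*Protocol*

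**What the plan says.** Under Outcomes, Secondary Outcomes, the protocol lists the metabolic markers as "Body weight, body composition, blood pressure, glucose, insulin, HbA1c, chemistry panel, lipids, and cognitive measures", followed by brain MRI. It lists the inflammation markers as "interleukin 1, interleukin 6, C-reactive protein, tumor necrosis factor-alpha, and WBC count with differential". HbA1c and the white-cell differential are therefore both named secondary outcomes. Table 1 schedules the venous draw at baseline, week 6 and week 12.

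Methods, Testing Visits, describes the handling of the blood in this order:

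- On tubes: "Appropriate sample tubes will be used for EDTA, sodium heparin, or serum for different analytes".
- On the outside laboratory: "A serum tube will be sent to Quest Diagnostics to assess standard chemistry panel", with liver enzymes, kidney function and lipids as examples.
- On processing: "Serum and plasma will be immediately centrifuged and aliquoted into tubes and stored at -80°C until subsequent analyses".
- On assays, after a single thaw: "assayed in duplicate for ketones, glucose, and insulin, which will be used to calculate an index of insulin resistance, and HbA1c".
- What is left of the serum and plasma is archived for later biomarker work.

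The text describes no whole-blood or packed-cell aliquot and no blood count.

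**The concern.** The assay list puts HbA1c on a specimen that cannot give it. Specimen handling is an instruction to site staff, so an analysis plan would not be expected to repair it.

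The error matters because it cannot be undone. An analyte that survives in frozen serum or plasma can still be assayed if someone notices its absence later. Red cells removed by centrifugation and not kept cannot be brought back. A participant handled this way would have no baseline HbA1c, and collecting whole blood correctly at weeks 6 and 12 would still give no change from baseline. The protocol hypothesises an improvement in metabolic health and wants mechanistic information for a later comparative trial. HbA1c is one of the markers meant to serve that aim.

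**Working it through.** The protocol gives no figure to reproduce, and the point depends on no sample size or power input. The check sets the outcome list against the specimen text.

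**Step 1: what HbA1c needs.** HbA1c is the glycated fraction of haemoglobin, which sits inside red cells. It needs whole blood or a red-cell lysate. This is general laboratory knowledge and is not stated in the protocol.

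**Step 2: what the protocol gives it.** The sentence before the assay list concerns serum and plasma that are centrifuged, aliquoted and frozen. The samples that are then thawed can only be those aliquots, and they contain no red cells.

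**Step 3: both ways of reading the assay sentence.** HbA1c comes after a relative clause, so the grammar is loose.

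| Reading | Consequence |
|---|---|
| HbA1c is a fourth assay, alongside ketones, glucose and insulin | Wrong specimen: no red cells |
| HbA1c is calculated from those three, as the insulin-resistance index is | Not a measurement of HbA1c |

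Neither reading gives a valid result.

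**Step 4: is there another source?**

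| Material described | Contains red cells? |
|---|---|
| Tube sent to the outside laboratory | No, it is serum, so an open-ended chemistry panel cannot include HbA1c |
| Frozen aliquots | No, serum and plasma |
| Archive | No, serum and plasma |
| EDTA tubes as drawn | Yes, until spun; but none is assigned to HbA1c, and the assay list places HbA1c elsewhere |

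**Step 5: the white-cell differential.** This needs fresh, unspun, anticoagulated blood. EDTA tubes are drawn. The text does not say that one is kept unspun, and it does not say that all are spun. It never lists the differential as a serum or plasma assay. The specimen is unstated rather than wrongly stated.

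**Step 6: how many draws are involved.** The protocol expects 30 to 60 participants (Recruitment) and three draws each (Table 1). The planned HbA1c measurements number between 30 × 3 = 90 and 60 × 3 = 180. These counts assume that every participant attends every draw. They are the number of planned measurements the sentence governs, not an estimate of data lost.

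**The case against.** The strongest reply is that this section is a summary and not a laboratory manual. The assay list is plainly incomplete: it also leaves out interleukin 1, interleukin 6, C-reactive protein and tumor necrosis factor-alpha, all named outcomes. EDTA tubes are drawn for different analytes, nothing says that cells are discarded, and the test-day figure is not shown in the text at hand. HbA1c may simply have been tacked on to a badly built sentence while the staff intend to use whole blood.

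Part of this stands. Careless drafting is a plausible explanation, and if whole blood is already kept in practice, no data will be lost. It does not rescue the text. HbA1c is not merely missing from the list; it is on the list, against the wrong specimen.

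The reply succeeds fully against a stronger reading that a reader might infer: that the white-cell differential cannot be obtained either, so that two outcomes are certain to be wholly missing in up to 180 samples. The documents do not support that. The provision of EDTA tubes leaves room for an unspun one, and an incomplete assay list cannot show that an unlisted test is impossible. The differential does differ from the cytokines and C-reactive protein in that stored serum or plasma cannot supply it later. That is a reason to state its specimen, not proof that it is lost.

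**Conclusion.** The HbA1c instruction is wrong as written. If staff follow it literally, this one secondary outcome is unavailable at baseline, week 6 and week 12, and the baseline value is beyond recovery. The conclusion rests on the general laboratory fact that HbA1c requires red cells, and on reading the thawed samples as the serum and plasma of the preceding sentence. No other antecedent is offered.

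The label covers HbA1c only. For the white-cell differential the protocol has a gap in detail, which alone would not count as an error.

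The consequence is limited. Completion, ketosis, PHQ-9 and HRSD do not depend on this specimen, and the trial is a single-arm pilot with a long list of secondary measures. The correction should be made before further baseline draws, because the harm would be irreversible and the remedy is small.

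**What to change.** Make two changes under Testing Visits:

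1. Remove HbA1c from the list of assays run on thawed serum and plasma.
2. State that at each draw (baseline, week 6, week 12) an unspun EDTA whole-blood tube or aliquot is kept for HbA1c, and name the laboratory that will run it.

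In the same sentence, state the specimen for the white-cell count with differential. The same fresh EDTA blood can serve both tests. Whether the count is done on site or by the outside laboratory is the sponsor's choice; the protocol only needs to say which.

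The cost is at most one more tube from the same venepuncture and the fee for routine tests. EDTA tubes, a phlebotomist and an outside laboratory are already in the plan. If whole blood is already being kept, the change is one of wording only. If it is not, participants already processed as written have no recoverable HbA1c for those draws, and the report should say so.

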inflammation in metabolically-impaired individuals^{12,14,23,24}. Elevations in a range of inflammation biomarkers has been associated with severity of depression^{25,26}.

Although KDs have been proposed as a treatment option for mental health disorders, including schizophrenia²³ and depression⁷, few human clinical trials have tested the efficacy of this eating pattern specifically in a population of adults with major depression. In patients with type 2 diabetes (n=262) prescribed a KD using a novel virtual care model (Virta Health), we observed significant improvements in depressive symptoms after 10-weeks, which were directly correlated with the degree of carbohydrate restriction and nutritional ketosis as assessed by blood concentrations of ketones^{27,28}.

IMPACT

The overarching goal is to perform a pilot study to: (1) demonstrate that a well-formulated KD can be implemented in a university counseling treatment program for major depression, and (2) test whether such a program results in reductions of symptoms of depression. We plan to recruit 60 students with major depression who will receive coaching and support on a KD over a 12-week period; this will demonstrate initial feasibility of the diet. We hypothesize that participants will demonstrate improvements in metabolic health, mental health, cognition, and brain function (using Magnetic Resonance Imaging; MRI)²⁹. The data from this pilot study will be used to generate effect size estimates to inform the design of an intervention study to compare efficacy of a KD to standard diet and/or other diet treatment strategies. The results from this open-trial will also be valuable for providing safety information and providing relevant mechanistic information regarding KD-induced improvements in depression.

RESEARCH STRATEGY

This will be a single arm prospective trial assessing feasibility of implementing a KD in up to 60 participants with depression over 12-weeks. Participants who are MRI eligible will also have the option to complete pre- and post-intervention brain MRI. After enrollment, participants will complete a battery of baseline tests. The intervention will last 12-weeks with the primary efficacy outcomes assessed bi-weekly and other secondary/exploratory outcomes assessed at time points detailed in **Table 1**. Participants will receive standard of care clinical treatment for depression through the OSU Counseling and Consultation Services (CCS) throughout the intervention.

OUTCOMES

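### Table 2 and the test-day text disagree on when cognition is tested at week 12, and any retest gain enters the cognitive effect size of this single-arm trial in full

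*Protocol*

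**What the plan says.** The Research Strategy section describes the design: "This will be a single arm prospective trial assessing feasibility of implementing a KD in up to 60 participants with depression over 12-weeks". There is no comparison group. The Impact section nevertheless states a direction for cognition: "We hypothesize that participants will demonstrate improvements in metabolic health, mental health, cognition, and brain function". Under Secondary Outcomes, cognition is one of the measured changes: "we will assess changes in a number of metabolic markers and cognitive markers of psychological health".

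Table 1 schedules cognitive testing at baseline and week 12 only. For the sequence within a test day there are two sources:

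- **Testing Visits text.** It opens with "subjects will arrive to the lab in the morning after an overnight fast" and goes through hydration, body mass, surveys, blood pressure, blood draw and DXA. It ends with "Finally, subjects will complete a battery of computerized cognitive tests". It makes no distinction between baseline and week 12.
- **Table 2.** At baseline, 3a covers the physical measures, including "Venous Blood Draw, Body Composition, and Blood Pressure", and 3b is "Cognitive testing". At week 12, 7a is "Cognitive Tests" and 7b holds the physical measures and blood draw.

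The section on neurocognitive test materials names the NIH Toolbox. It gives the standardized neuropsychological sub-tests only as examples and makes some computer-based tests optional. It does not mention alternate forms, a familiarisation session or a correction for practice. Practice trials are described for the gradCPT alone, to confirm that the instructions are understood.

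**The concern.** A pre-post comparison relies on both measurements being taken in the same way. If staff work down Table 2, cognition follows an hour of physical measures and a blood draw at baseline and precedes them at week 12. Time of testing, fatigue and recent venepuncture would then differ between the two occasions, and a single-arm trial has no comparison that would remove the difference.

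Repeat testing raises a second problem whichever order is used. A participant may score better the second time through familiarity alone. A control group would show that gain and allow it to be subtracted; here it cannot be told apart from an effect of the diet. The protocol's stated product is effect sizes to inform a later comparative study, so a cognitive effect size that contains practice would be carried into that planning.

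**Working it through.** **Step 1. The two descriptions of the order.**

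| Source | Baseline | Week 12 |
|---|---|---|
| Testing Visits text | cognition last | cognition last (same text) |
| Table 2 | 3a physical and blood draw, then 3b cognition | 7a cognition, then 7b physical and blood draw |

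The sources agree at baseline and conflict at week 12. Table 2 allots 1 hour to each block, so under its listing cognition would start about 1 hour later in the session at baseline than at week 12.

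**Step 2. Do the letters in Table 2 mean sequence?** The evidence goes both ways. For sequence: 2a (consent and interview) must come before 2b, because the eligibility decision sits between them, and 3a then 3b matches the text. Against: the table is not said to be chronological. Within 3a, blood pressure is listed after the blood draw, while the text measures it before. The lettered MRI rows (3d, 7c) are scheduled separately and in another building. Fig. 2, the test-day timeline, is not available in the copy reviewed. The contradiction is therefore established, and a changed order is not.

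**Step 3. Number of exposures.** Table 1 gives two cognitive sessions, and Table 2 lists none at week 6. One sentence under Testing Visits puts all other outcomes at baseline, 6 and 12 weeks. Read literally, that would add a third session and more practice.

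**Step 4. What a retest gain would do.** The protocol gives no power, significance level or effect size for cognition, so there is no figure to reproduce. The following is an illustration.

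Inputs from the protocol: 30 to 60 enrolled (Recruitment); more than 80% expected to complete (Primary Outcomes). At exactly 80%:

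- 0.80 × 30 = 24 completers
- 0.80 × 60 = 48 completers

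Assumptions, not in the protocol: no diet effect; a pure retest gain d of 0.1 to 0.3 SD of the change score; a paired test at two-sided 5%.

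Formula: z = d × √n, with √24 = 4.90 and √48 = 6.93. The chance of a significant result in the direction of improvement comes from the noncentral t distribution with n − 1 degrees of freedom and noncentrality d√n.

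| d | z, n = 24 | chance, n = 24 | z, n = 48 | chance, n = 48 |
|---|---|---|---|---|
| 0.1 | 0.49 | 7% | 0.69 | 10% |
| 0.2 | 0.98 | 15% | 1.39 | 27% |
| 0.3 | 1.47 | 29% | 2.08 | 53% |

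The nominal rate in that direction is 2.5%. By the normal approximation, z reaches 1.96 at d = 1.96/4.90 = 0.40 with 24 completers and at d = 1.96/6.93 = 0.28 with 48. Most of the assumed range therefore falls short of significance. The bias in the estimated standardized change is d itself at any sample size, and that is what matters for a study whose product is effect sizes.

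**The case against.** The case on the other side is substantial. The only prose description gives a single order for all test days, and the reversal at week 12 may be no more than careless labelling in Table 2. Practice is a limitation of every uncontrolled pre-post study, and the protocol openly calls itself a pilot and an open trial. Cognition is secondary. The analysis section names a model for depression scores only and states no test for cognition. The choice of test forms may also sit in a testing manual.

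Several stronger readings are tempting, and the documents do not support them:

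- **That cognitive change is confounded by order.** This would require Table 2 to be chronological, which is not stated, and the timeline figure is not available to check.
- **That the order change favours apparent improvement.** Nothing in the protocol gives the direction or size of an order effect.
- **That participants are fasted at one visit and fed at the other.** The overnight fast applies to test days generally, and no meal is described before cognition at either visit.
- **That a false finding would be declared significant.** No significance test for cognition is planned, so the chances shown above describe a hypothetical analysis.

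What the objection leaves standing is narrower. Two parts of one protocol give different orders for a pre-post outcome. A directional hypothesis on cognition is stated with no comparison group, and nothing described would limit practice.

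**Conclusion.** The point holds in two parts. First, Table 2 at week 12 contradicts the test-day text. Staff who follow the table as listed would run the two cognitive assessments under different conditions. Whether they would, and what it would do to the scores, cannot be determined from the protocol. Second, any retest gain enters the cognitive effect size in full. Its size is unknown; the z values of about 0.5 to 1.5 (24 completers) and 0.7 to 2.1 (48 completers) rest on an assumed d of 0.1 to 0.3, exactly 80% completion and no diet effect.

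The consequence is modest. Cognition is a secondary outcome, and the feasibility and depression outcomes are untouched. The point is still worth settling before testing starts, because a difference in test conditions cannot be repaired in the analysis.

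**What to change.** 1. Reconcile Table 2 week 12 with the Testing Visits text and Fig. 2, so that cognition has the same position at baseline and week 12. Swapping the two week 12 rows would match the text. Cost: none.
2. Fix the cognitive battery in advance and give the same tests on both occasions, with alternate forms at week 12 where the instrument has them. Cost: selecting the forms.
3. Align the sentence that places all other outcomes at weeks 0, 6 and 12 with Table 1, so that the number of cognitive sessions is clear. Cost: one sentence.
4. State that cognitive results will be reported as uncontrolled pre-post change that includes practice, not as evidence of a diet effect, and carry that caveat with any effect size used to plan the next study. Cost: a more modest claim about cognition.

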- Disordered eating, as evidenced by meeting criteria for Anorexia Nervosa, Bulimia Nervosa, Binge Eating Disorder, Other Specified Eating Disorder, Unspecified Eating Disorder, or Avoidant Restrictive Eating Disorder during the SCID-5 interview at baseline testing.
- Substantial imminent risk of suicide as assessed during the SCID-5 interview.
- Body mass index (BMI) < 20 kg/m²
- Habitual consumption of a structured low-carbohydrate diet in the last 6-months
- Gastrointestinal disorders or allergies that would prevent adherence to prescribed diets
- Alcohol consumption in excess of 3 drinks/daily or 14 drinks/weekly
- Diagnosed diabetes, liver, kidney, or other metabolic or endocrine dysfunction, or use of diabetic medications other than metformin
- Inability to access or prepare appropriate KD foods/meals
- Pregnant, lactating, or planning on becoming pregnant during the study
- Unwilling to perform finger-stick blood testing or continuous glucose/ketone monitoring

Exclusion for optional MRI:

- The CCBBI screening form (<https://redcap.osumc.edu/redcap/surveys/?s=N3XJ4WC7T9>) will be used to assess MRI eligibility. Endorsement of items that contraindicate MRI will serve as exclusion criteria (pacemaker, stint, claustrophobia, etc.).

Recruitment:

OSU students will be recruited through the Office of Student Life's CCS, and through the recommendations of the 50+ counselors associated with the Health and Wellness Center who are

charged with the care and wellbeing of OSU students experiencing major depressive symptoms. All potential participants must be currently enrolled with the Student Life’s CCS. Initial screenings for qualifying inclusion and exclusion criteria will be conducted by [name] and his team. We expect to enroll between 30 and 60 participants. The total number of students who received clinical services through CCS during the 2020-2021 academic year was 5,488. Thus, recruiting 30 – 60 participants who meet inclusion and exclusion criteria is an achievable goal.

METHODS

Study overview:

[figure not shown]

Fig. 1 Experimental Approach.
Created with BioRender.com

Study Procedures

The timeline of various study procedures is detailed in **Table 1**.

Table 1: Study Assessment Timeline

Test	Week												
	BL	1	2	3	4	5	6	7	8	9	10	11	12
SCID-5 RV ¹	X												
WHO-5 ²	X		X		X		X		X		X		X
PHQ-9 ³	X		X		X		X		X		X		X
Depression Scale ⁴	X						X						X
CGM/CKM ⁵	X	X				X	X					X	X
Finger Stick BHB ⁶	X	X	X	X	X	X	X	X	X	X	X	X	X

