Patient demographic and characteristics information, pre- and post-intervention depression scores and other outcomes will be summarized for the KD group at every time point. Considering this is a pilot feasibility study, we will focus on calculating effect sizes. Changes in depression scores within the KD group will also be evaluated using a linear mixed model for repeated measures, with the baseline score potentially included as a covariate to control for baseline variability. The linear mixed models (Multi-level Model, MLM) will allow us to easily handle missing data (assuming Missing-at-random) and estimate within group effects from the same model. These models can also easily handle co-variates and are robust to violations of normality. Normality and heteroscedasticity will be checked using residual plots. All data that are non-normal may be either suitably transformed (e.g., log, Box-Cox) or analyzed using non-parametric methods (Kruskal-Wallis test).

Incidental Findings

There may be incidental findings observed on MRI, cognitive, and fitness assessments. For each type of assessment, the participant’s primary care physician will be contacted within 30 days of incidental finding detection. Each participant will provide contact information for their healthcare provider at entry of the study.

STUDY MONITOTRING

Concomitant Medication/Supplements and Treatment

All concomitant medications/supplements used 1 month prior to Screening Visit and during the study will be reported to the study personnel for assessment and recorded in the participant’s study documents.

CONDUCT OF THE STUDY

1. Ethics and Regulatory Considerations

This study will be conducted according to Good Clinical Practice Guidelines, the Declaration of Helsinki (2004) and United State Code of Federal Regulation Title 21. Signed written informed consent for participation in the study will be obtained from all participants before protocol-specific procedures are carried out. Participants will be informed of their right to withdraw from the study at any time. Participants will be informed that their participation in the study is completely voluntary, personal information will be both de-identified to preserve anonymity.

2. Institutional Review Board

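### The only rank test named, Kruskal-Wallis, needs independent groups, but this single-arm trial measures the same people repeatedly, so its p-values would be invalid and, with positive within-person correlation, conservative

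*Protocol*

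**What the plan says.** The design is stated under Research Strategy: "This will be a single arm prospective trial assessing feasibility of implementing a KD in up to 60 participants with depression over 12-weeks". No control group, subgroup contrast or other between-person comparison is described anywhere.

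Measurement is repeated on the same participants. Under Testing Visits: "Other outcomes will be assessed at baseline, 6- and 12-weeks at a single visit in the PAES Building". The number of visits varies by outcome in Table 1: PHQ-9 and WHO-5 have seven time points, HRSD and most blood and body measures have three, and cognition and MRI have two (baseline and week 12).

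Under Data Analysis and Statistical Methods, the emphasis is on estimation: "Considering this is a pilot feasibility study, we will focus on calculating effect sizes". For depression: "Changes in depression scores within the KD group will also be evaluated using a linear mixed model for repeated measures". The mixed model is also the stated means of dealing with missing visits: "The linear mixed models (Multi-level Model, MLM) will allow us to easily handle missing data (assuming Missing-at-random"). After a sentence on residual checks comes the fallback: "All data that are non-normal may be either suitably transformed (e.g., log, Box-Cox) or analyzed using non-parametric methods (Kruskal-Wallis test"). No signed-rank, Friedman or other paired rank method is named.

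**The concern.** Kruskal-Wallis assumes that the samples being compared are independent. With one arm, the only samples it could compare are the visits, and these come from the same people. The named test therefore fits no comparison that the protocol describes, and it conflicts with the preceding sentences of the same section, which treat the data as repeated measures.

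The direction of the error is predictable. Repeated scores or biomarkers in one person are normally positively correlated. Kruskal-Wallis then overstates the variability of the difference between visits, so p-values are too large and real change can be missed. Exposure is greatest for secondary outcomes (insulin, inflammatory markers, cognition, MRI), because the mixed model is specified for depression scores only. The fallback sentence covers all non-normal data, however, so PHQ-9 or HRSD could reach it too.

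**Working it through.** The protocol states no alpha, power, effect size, SD or within-person correlation, so there is no figure of its own to reproduce.

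**Inputs from the protocol.** Enrolment of 30 to 60 (Recruitment); completion above 80% (Outcomes), giving at the lower limit 0.80 × 60 = 48 or 0.80 × 30 = 24 completers; two, three or seven visits (Table 1); about 15 MRI volunteers (MRI Image Acquisition).

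**Assumptions.** Two-sided 5% level; equal correlation ρ between visits unless stated; changes in units of the underlying SD.

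**Step 1: size, analytically, two visits.** An unpaired test takes the variance of the mean difference as 2σ²/n. Its true value is 2σ²(1 − ρ)/n. True size = 2[1 − Φ(1.96/√(1 − ρ))].

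- ρ = 0: 5.0%
- ρ = 0.3: 1.96/0.837 = 2.34, size 1.9%
- ρ = 0.5: 1.96/0.707 = 2.77, size 0.6%
- ρ = 0.7: 1.96/0.548 = 3.58, size 0.03%

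**Step 2: size by simulation, log-normal data, three visits, n = 60.** Kruskal-Wallis rejects in 5.1%, 1.3%, 0.3% and under 0.1% of null trials at ρ = 0, 0.3, 0.5 and 0.7. Only negative correlation makes it too liberal (about 6% to 8.5% at ρ = −0.1 to −0.2 across the settings run), which is implausible here.

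**Step 3: a score that a transform cannot normalise.** Integer score = 3 + 4z, rounded down and limited to 0–27. The share at zero is P(3 + 4z < 1) = Φ(−0.5) = 31%. Two visits:

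| Completers | ρ | Change (SD) | Kruskal-Wallis | Signed-rank |
|---|---|---|---|---|
| 48 | 0.5 | 0 | 1.3% | 5.1% |
| 48 | 0.5 | 0.2 | 8% | 23% |
| 48 | 0.5 | 0.4 | 42% | 66% |
| 48 | 0.5 | 0.6 | 82% | 93% |
| 48 | 0.5 | 0.8 | 98% | 99% |
| 48 | 0.1 | 0.4 | 44% | 46% |
| 48 | 0.3 | 0.4 | 41% | 52% |
| 48 | 0.7 | 0.4 | 41% | 84% |
| 24 | 0.5 | 0.4 | 16% | 36% |

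**Step 4: log-normal data, ρ = 0.5, change 0.4 SD.**

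- Two visits, n = 48: Kruskal-Wallis 46%, signed-rank 72%, paired t-test on logs 77%.
- Three visits, n = 60: Kruskal-Wallis 38%, Friedman 65%.
- Seven visits, n = 60: Kruskal-Wallis 25%, Friedman 74%.
- Two visits, n = 15 (the MRI subset): Kruskal-Wallis 12%, signed-rank 28%.

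The paired methods held their size at 4% to 6% under equal correlation. With strong serial correlation over seven visits, Friedman's size rose to between 6.4% and 7.3%.

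**The case against.** The strongest reply concerns weight. The sentence is permissive and offers transformation as an equal alternative. The pilot is meant to yield effect sizes, sets no significance-based decision rule, and has a mixed model for depression that the protocol regards as tolerant of non-normality. A conservative optional p-value creates no false claim of benefit. All of this stands, and it limits the importance of the point.

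The numerical scenario can also be questioned. A score with 31% at zero at baseline cannot represent PHQ-9 in students with confirmed major depression, and no listed outcome is shown to have that shape. That is fair: the figures illustrate what happens when a transform fails and predict nothing about a particular endpoint. Log-normal markers can be rescued by the log transform named in the same sentence. The conservatism depends on positive correlation, and at ρ = 0.1 the loss is negligible.

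A separate analysis plan might name a different test. That would not correct the protocol, which names one rank method, and an unsuitable one. Had it mentioned only non-parametric methods in general, there would be nothing to raise.

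**Conclusion.** The concern holds. Kruskal-Wallis is wrong for every comparison the protocol describes, because one group measured repeatedly supplies no independent samples. Under positive within-person correlation the test is conservative. At ρ = 0.5 with 48 completers and a floored score, true size is 1.3% and power at 0.4 SD falls by 24 percentage points (66% to 42%). The loss is material for small to moderate changes at correlations of 0.3 or more, and small for large changes or low correlation. These sizes rest on assumed effects, correlations and distributions; that the test does not fit the design rests on none of them.

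The damage is confined to outcomes sent to the fallback. The mixed model itself, the effect-size estimates, and the completion and ketosis counts are unaffected. It should be corrected, but it does not threaten the trial's main purpose.

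**What to change.** Replace the parenthesis naming Kruskal-Wallis with: *Wilcoxon signed-rank test on the within-person change from baseline to week 12, with the Hodges-Lehmann estimate and 95% CI; for three or more time points, a rank-based or bootstrap repeated-measures model that keeps participants with missing visits, or the Friedman test where visits are complete.* The estimate and interval suit a pilot focused on effect sizes. If a shorter text is wanted, naming a paired rank method is enough to remove the error.

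No new data are needed. The costs are:

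- **Friedman drops anyone with a missing visit.** With 60 people, seven PHQ-9 visits and 10% of post-baseline visits missing at random, complete rows are 60 × 0.9⁶ ≈ 32. At ρ = 0.5 and a linear decline to 0.4 SD (log-normal data), its power falls from 74% to 42%. A rank model with participant effects goes from 79% to 76%, and signed-rank from baseline to week 12 goes from 82% to 78%.
- **Signed-rank excludes anyone without a week-12 value**, assumes roughly symmetric differences, and in its standard form discards tied pairs. In the floored scenario (ρ = 0.5, decline 0.4 SD) about 28% of pairs are tied, so the handling of ties should be stated.
- **The rank model takes slightly more programming.**
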